9.2 Description of the intervention

1. Provider Medication Alert: If a prescribing clinician attempts to place a new order or change an existing prescription for one of the study medications (Table 1), an EHR-generated alert will notify the provider that the medication requires patient counseling. This alert will contain a brief description of the top risks or side effects that patients may experience while taking this medication; this information is directly derived from the FDA-approved Medication Guide for the drug. The pop-up will also include an html link to the 1-page Med Sheet, which they can use to further inform their counseling.

2. Automated Delivery of Med Guide Summary: When the patient leaves an encounter and checks out, the medication order in Centricity will automatically cue printing of the 1-page Med Guide Summary.

STU#: 00201638

3. IVR Follow-Up Phone Assessment: One day after a patient's baseline interview (which will occur within 1-30 days post-visit), the patient will be prompted to call into the automated IVR system. The goal of the IVR call is to confirm patients' understanding and safe use of the prescribed high-risk medication they are taking, and to screen for any adverse drug events that may arise from having taken the medicine.

The call will investigate content areas that will be standard across all medications under study: 1) medication recognition, 2) medication fill (and fill barriers, if applicable), medication adherence (and adherence barriers, if applicable), perceived effectiveness, and side effects experienced. The IVR content was derived from the Med Guide Summaries. Patients are able to speak their responses as "yes", "no", or "do not know" or use their keypad.

To facilitate the call, patients will be sent (via text or phone call) a call-in number for the IVR system so that they are able to make the call at their convenience. The text with the call-in number will be sent on the day following the patient's baseline interview. (The day lag is needed so that the participant's medication data can first be uploaded to the IVR system in preparation for the call).

If subjects have not used the system after one day, a reminder text message, again including the call-in number, will be sent by the RA at Northwestern. If subjects have not used the system after two days, the RA at Northwestern will call the patient to remind them to call into the system and to ensure they have the call-in details.

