9.3 Research procedures

Research activities will include a baseline interview and follow-up interviews at 4 weeks and 3 months; all interviews will be conducted over the phone. Patients in the intervention arm will receive a prompt to call into an interactive voice response (IVR) system one day after their baseline interview (so 2-45 days after their index clinic visit) to confirm understanding and safe use of their medicine (described in 9.2 Description of the Intervention).

Pilot Testing. We will pilot-test the study battery, protocol and patient materials among English and Spanish-speaking patients at Alliance sites. Cognitive interviews will be conducted among a convenience sample of 30 patients (n=15 per language) that meet full eligibility criteria. We will obtain average interview completion times, elicit patient comprehension, and acceptability of the interview and patient materials. Any identified problems will be analyzed and modifications made as appropriate. Pilot patient data will be used if no significant changes are made to the study.

STU#: 00201638

Initial Interview. After confirming patient eligibility, obtaining verbal consent, and receiving patient prescription information, the RA will administer the baseline interview via phone. As long as the patient is still taking or planning to take the prescribed medicine, the patient will then be eligible for follow-up interviews and, if in the intervention arm, to receive the remaining EMC2 components (IVR, nurse follow-up).

Follow-up Interview #1. The first follow-up interview will be scheduled at the time of the baseline interview for 4 weeks later.

Follow-up Interview #2. The second follow-up interview will be scheduled at the time of the 4-week interview for 8 weeks later.

Spanish Language Materials. All study materials (screener script, consent form, battery, IVR call) have been or will be translated into Spanish to accommodate Spanish speakers. Several of the measures in the battery already have validated Spanish versions; everything else has been translated by Research Support Services, led by [name], using a modified committee approach. In this translation approach, three bilingual, bicultural translators independently translate one-third of each document into Spanish, then discuss the resulting texts and reach an agreement on best words/phrases for the final product. The strength of this approach has been recognized by the Census Bureau Guidelines for Survey Translation.

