Adverse Drug Events (ADE). ADEs will first be assessed using a validated questionnaire administered by the RA during the 3-month follow-up phone call. If the patient reports that their medication is finished at the 1-month interview, the ADEs will be assessed using the same approach at the 1-month interview. [name] will review all self-reported ADEs to determine whether these symptoms could reasonably be linked to one of the prescribed high-risk medications. We will then determine whether confirmed ADEs were reported to the clinic via the IVR system by reviewing IVR data. Drs. [name] and [name] will oversee this process.

Fidelity Outcomes:

- Provider Counseling. We will ask patients (yes/no) whether their prescriber/nurse/pharmacist counseled them. We will also ask the Health Literacy supplemental items of the Consumer Assessment of Health Providers Survey (CAHPS) to evaluate the extent and quality of provider verbal counseling on Rx medications. Prescriber/nurse counseling will be assessed immediately following the appointment (during the baseline interview); pharmacist counseling will be assessed at baseline if the prescription has been filled by that time, otherwise on the 4-week call.
- Receipt of Med Guide Summaries. We will ask patients in both arms whether they received any written information from their provider.
- Receipt of IVR Calls and Nurse Counseling. We will collect data from the IVR to determine whether interviews were completed and whether responses warranted nurse counseling.
- Frequency of Clinic Follow-Up. We will ask patients (yes/no) whether someone from the clinic contacted them following any concerns reported to the IVR system.
- Helpfulness of EMC2 components. Intervention patients will be asked (yes/no) whether they received Med Guide Summaries, IVR calls, and follow-up nurse calls and how helpful they were. "On a scale of 1 to 10, 1 being not helpful at all and 10 being extremely helpful, how helpful was...?"
- Provider experience. We will ask providers at intervention clinics about their use of the BPA pop-ups (if they saw them and if so, how they used them), med sheets (if they noticed patients receiving them), and IVR (if they received any feedback from the patients about the call and if they saw any of the IVR reports).

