11.5 Study-wide data management

Data Access: Only authorized personnel listed on the IRB will have access to the data.

Data Storage: NU: Data will be stored on the Northwestern server for the length of the study. All identifiable information will be deleted upon completion of the study. BMC: Identifiable data will be stored in BMC's HIPAA-compliant REDCap database until the IVR call is completed or for a maximum period of 6 weeks. The REDCap database is backed up by a secure BMC server for a period of 3 days. After 3 days, data is deleted. HL7 text files will be stored (for IVR calls requiring a lab report) in the Mirth database for 7 days and then deleted.

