Time-sensitivity: Subjects become eligible at the time they are newly prescribed one of the study medications, with primary outcomes including their proper understanding and use of the medication, near to the time of fill and for the following 3 months. Therefore it is imperative that we are able to recruit them within the first week of their new prescription to launch the intervention. Receiving data from the EHR to identify and recruit eligible patients and consenting via phone is the only viable solution given the time constraints of the intervention. The IVR intervention call is triggered from completion of baseline (as early as 1 day after the baseline interview and within 4 weeks of the clinic visit), with the aim to reinforce learning and identify medication errors, including serious side effects. Given the range in duration of the medications included, including a number of short duration medications, it would not be possible to wait for a written HIPAA consent to be mailed by participants. It is imperative that the IVR functions while participants are currently taking the medications to accurately capture side effects and medication issues.

Resource limitations: While we did consider the possibility of on-site recruitment or leveraging clinic staff to support consent and/or data collection efforts, this is not possible. Working within the confines of the financial limits of the R01 mechanism, we cannot afford the resources to have staff in all of the 12 geographically diverse locations. Potentially eligible patients cannot be pre-identified, as patients only become eligible once they are prescribed a medication from the study list. It would also be too great a burden to ask clinic staff to remember to disperse a consent form and written HIPAA at the time of prescribing (this has been discussed with clinic sites), and an alert cannot also be included to that regard. Asking clinic staff to distribute consent forms would also require all staff at each clinic site to become research study personnel authorized to consent participants. Training each nurse and care coordinator who could potentially interface with patients once triggered would be an impossible task, especially given the shift-work nature of these positions. Any other efforts to have the patient provide written HIPAA consent would place undue burden on the patient for participating.

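### One IVR call the day after baseline is matched to ADEs collected at up to 3 months, with no onset date, call date or matching rule described, so detection credited to the call under H3 cannot be verified

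*Combined protocol and SAP*

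**What the plan says.** Section 9.2 ties the IVR step to the baseline interview, which takes place 1 to 30 days after the visit. On the next day, "the patient will be prompted to call into the automated IVR system". The patient makes the call, on a number sent in advance "so that they are able to make the call at their convenience". Reminders follow only while the patient has not yet used the system, and no second round is scheduled. Answers are yes, no or do not know. A flagged concern goes to the clinic as a report giving the type of concern.

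The timing of the prompt relative to the index visit appears in three forms: days 2 to 31 by implication in Section 9.2, "one day after their baseline interview (so 2-45 days after their index clinic visit" in Section 9.3, and "as early as 1 day after the baseline interview and within 4 weeks of the clinic visit" in Section 29.

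Identifiers at the IVR host are held "until the IVR call is completed or for a maximum period of 6 weeks" (Section 11.5). Sections 10.1 and 11.3 keep the IVR responses with a record or study ID. Neither says that the call date is kept with them.

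On ADEs, Section 9.4 states: "ADEs will first be assessed using a validated questionnaire administered by the RA during the 3-month follow-up phone call". Patients who have finished the drug by the 1-month interview are assessed then. Self-reported ADEs are reviewed for a plausible link to a study drug, and after that: "We will then determine whether confirmed ADEs were reported to the clinic via the IVR system by reviewing IVR data". Section 11.2 defines detection differently, as events in the medical chart divided by events reported at 3 months. Section 25.3 says the research team has no access to medical records, and the data sources listed in Section 9.4 are interviews, IVR responses and provider surveys.

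**The concern.** H3 says that ADEs will be detected at a higher rate under EMC2. The only detection procedure the documents describe is the comparison of ADEs recalled at up to 3 months with answers given on one early call. That comparison needs two facts the text does not provide for: whether the ADE had begun when the patient called, and whether the side effect mentioned on the call is the same event.

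Two errors follow, in opposite directions.

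- **False credit.** A patient who flags one complaint on the call and later has another ADE can be counted as having had that ADE detected. Usual care has no IVR, so this can happen only in the EMC2 arm and inflates its rate.
- **Dilution.** An ADE that begins after the call cannot be caught by it but stays in the denominator, which pulls the difference between arms toward zero.

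Without onset, the two cannot be separated or sized. A null H3 result could not be traced to the timing of the call, and a positive one could not be shown free of false credit. Onset that is not asked at the interview is hard to recover later.

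**Working it through.** **Inputs.** From Section 11.2: usual-care detection 21% (35 of 166 events); 96 patients with an ADE per arm (20% of 480); detectable difference 18.2 points. The 80% power and 5% type I error are stated there for the knowledge outcome. I take them to carry over, with a two-sided test.

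**Step 1: reproduce the plan's figure.** For two independent proportions with unpooled variance and no design effect, solve

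d = (1.96 + 0.842) × √{[0.21 × 0.79 + (0.21 + d)(0.79 − d)] / 96}.

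This gives d = 0.1818, or 18.18 points, which matches 18.2. A pooled variance gives 18.46. Power at 21% against 39.2% is 80.1% unpooled and 79.0% pooled. Nothing in the calculation refers to when an ADE begins.

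**Step 2: dilution.** Let s be the share of ADEs that begin after the call. Suppose EMC2 adds 18.2 points for the others and nothing for these. The overall difference is 18.2 × (1 − s). The right-hand columns show what remains if only ADEs before the call are analysed, with 96 × (1 − s) per arm. All figures use the unpooled formula.

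| s (assumed) | Overall difference (points) | Power, 96 per arm | Per arm, onset before call | Detectable difference in that subset (points) |
|---|---|---|---|---|
| 0% | 18.2 | 80% | 96 | 18.2 |
| 25% | 13.7 | 57% | 72 | 21.1 |
| 50% | 9.1 | 31% | 48 | 26.1 |
| 75% | 4.6 | 11% | 24 | 36.6 |

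**Step 3: is that range of s reasonable?** The documents give no onset pattern, so this step is illustrative. Section 9.3 puts the last interview 4 + 8 = 12 weeks (84 days) after baseline. A baseline on day 7 means a prompt on day 8 and a window of 91 days; a baseline on day 30 means a prompt on day 31 and a window of 114 days.

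- Uniform onset: 8/91 = 9% precede a day-8 call and 31/114 = 27% precede a day-31 call, so s is 91% and 73%.
- Early onset (exponential, mean 30 days, truncated at the window): (1 − e^(−8/30)) / (1 − e^(−91/30)) = 0.234/0.952 = 25%, and (1 − e^(−31/30)) / (1 − e^(−114/30)) = 0.644/0.978 = 66%, so s is 75% and 34%.

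Patients assessed at 1 month have a shorter window and a smaller s. A range of 25% to 75% is not extreme, but s could lie outside it.

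**Step 4: false credit.** With 96 patients with an ADE per arm, each otherwise-missed ADE wrongly credited to the call adds 1/96 = 1.04 points to EMC2. The detectable difference corresponds to 0.182 × 96 = 17.5 such credits. The documents give no basis for estimating how many would occur.

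Steps 1, 2 and 4 treat each patient with an ADE as one independent unit.

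**The case against.** The strongest reply is that a strategy with a single call really does miss later ADEs, so a smaller H3 difference is the true effect and not bias. That stands. It is why the all-ADE comparison should remain the main analysis. H3 also tests the whole EMC2 arm. Counseling and the Med Guide Summary may prompt patients to report, and IVR callers are told to phone the clinic with concerns. Late ADEs can therefore still reach the clinic, and the reach of the call is not a ceiling on the H3 effect.

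A reader might go further and infer three things that the documents do not support.

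- *Late ADEs count against EMC2.* Under the chart definition in Section 11.2 they sit in both arms' denominators and dilute the difference. Under the IVR definition in Section 9.4, usual care scores zero by construction, so the comparison favours EMC2.
- *No match to the call can be checked.* Responses and an ID are kept, and a review is planned, so a patient-level match is possible. What cannot be established from the data described is time order and whether it is the same event.
- *Onset is not collected.* The text is silent. The questionnaire is called validated but is neither named nor shown, and it may ask for onset.

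Two further points limit the weight of the concern. ADEs are a safety endpoint (Section 8.2) and the sample size rests on knowledge. Timely detection appears in the rationale (Section 2.3), whereas H3 concerns the rate of detection.

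**Conclusion.** The point holds as a gap in measurement and definition. The documents describe one early call, later ADE collection, and no onset date, retained call date or matching rule. As Section 9.4 is written, a flag can be credited to the wrong ADE in the EMC2 arm only, while late ADEs dilute the comparison.

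The 18.2-point figure is correct on its own terms but makes no allowance for either effect. If 25% to 75% of ADEs begin after the call and EMC2 adds nothing for them, the expected difference is 13.7 to 4.6 points and power is about 57% to 11%. Those figures rest on the assumed share and on no gain by other routes; any such gain would soften them. False credit works the other way and has no estimate.

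This does not invalidate H3. It means that an H3 result in either direction would be hard to interpret, when a small addition at interview would prevent that.

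**What to change.** 1. Record the onset date, or weeks since starting the drug, for each reported ADE in both arms. If the questionnaire already asks this, say so.
2. Keep the IVR call date with the retained responses.
3. State the matching rule: an ADE is IVR-detected only if its onset precedes the call and, where the IVR data allow, the symptom matches.
4. Reconcile the two definitions of detection. The Section 9.4 definition is zero by construction in usual care. The Section 11.2 definition needs a chart source that Sections 9.4 and 25.3 do not provide. If chart entries are used, apply the same time-order rule to them in both arms.
5. Keep the all-ADE comparison as the main H3 analysis. Add a descriptive split by onset before or after baseline + 1 day, an anchor that exists in both arms.
6. Reconcile the three statements of the call window in Sections 9.2, 9.3 and 29.

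The cost is one question per reported ADE, one retained date and one table. Recalled onset is approximate. Symptom matching depends on detail in the IVR data that the documents do not describe. The split is too small for formal testing: at 50% late onset, 48 patients per arm remain and the detectable difference is about 26 points.

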3.1 Methods of screening for eligibility

Patients will be initially screened for eligibility by Alliance's data pull and further screened over the phone by Northwestern Research Assistants (RAs).

Screening by Alliance. Alliance will send information to Northwestern on patients who meet the following conditions: (1) newly prescribed (i.e. had not been prescribed at Alliance within the previous two years) one of our study medications, (2) preferred language listed as English or Spanish, (3) age as of clinic visit > 21 years, (4) clinic visit occurred at a participating health center location (7 clinics associated with Near North Health Services Corporation).

Screening by Northwestern. Northwestern Research Assistants (RAs) will call those patients identified by Alliance and further screen them by asking eligibility questions and screening for cognitive impairment, in alignment with the inclusion and exclusion criteria (3.2).

We will receive patient information from Alliance in one of two ways:

Method 1- Each morning, Research Assistants (RAs) at Northwestern University will be able to access an SSRS report on a secure platform (Alliance SharePoint) showing a list of patients triggered as potentially eligible during a clinic visit on the day prior. The report will show the patient's contact information necessary for outreach for the purpose of screening (record id, first and last name, date of birth, clinic name, phone number, preferred language, and date of index clinic visit), but will not include the patient's medication information necessary for conducting the baseline interview. The RA will then call each patient, ask the few remaining eligibility questions to complete the screening process, invite the patient to participate, and obtain informed consent over the phone. The RA will then schedule a time to call the patient back for the baseline interview the next day (or as soon as possible thereafter). At the end of each day, the RA will upload a list of newly consented patients to Alliance Sharepoint, prompting Alliance to send medication information for those patients the following morning.

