Method 2- Each morning, Research Assistants (RAs) at Northwestern University will receive, via file sent to a secure ftp site, a list of patients triggered as eligible during a clinic visit on the day prior. The report will show the information needed to contact the patient and conduct the baseline interview (same data as listed in method 1, plus the name(s) of any study medications prescribed during the visit, the associated sig(s), prescriber name, and regular physician name). With this method, RAs will be able to conduct the baseline interview during the same phone call, immediately after screening and consenting the patient. This method would also allow the RA to explain to the potential participant which of their prescribed medicines would be the subject of the interviews and to confirm that the medication was actually prescribed, eliminating any confusion.

STU#: 00201638

Automatic exposure to part of intervention. Clinics will be randomized either to the intervention arm or to usual care. All patients who see a prescriber at a clinic site randomized to the intervention arm and who receive a prescription for one of the study medications (Table 1) will automatically receive some components of the intervention during their clinic visit (provider counseling, Med Guide Summary), regardless of whether or not they meet further screening criteria. This randomization and recruitment process will ensure that recruited patients may receive all in-clinic EMC2 components on the day they receive a prescription for a study drug. It will also result in a trickle down of some components of the EMC2 Strategy being given to patients seen at the intervention clinic site, but not enrolled in the study for follow-up purposes (EHR tools, but not IVR or nurse follow-up). This specific strategy of “turning on” an EHR intervention with provider or clinic level randomization has been previously approved by the IRB at Northwestern University for three other AHRQ funded grants [P01HS021141-01, 1U19HS021093-01 & 1R18HS017220-01]. Prescribers at these intervention sites will be made aware that the EHR tools have been activated, with the understanding that the tools themselves are educational in nature and will have minimal, if no effect on patient care and clinic workflow.

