3.2 Inclusion and exclusion criteria

Inclusion Criteria (Patients). To be eligible to enroll in the study, patients must attend one of the seven randomized clinics associated with the Alliance-affiliated health center Near North Health Service Corporation. They must also meet all of the following criteria: 1) age 21 and older; 2) English or Spanish speaking; 3) have received a new or changed prescription (i.e. had not been prescribed at Alliance within the previous two years) for one or more of our study medications (Table 1); 4) have a personal phone line (land or mobile).

Inclusion Criteria (Providers). To be eligible to complete the provider survey, providers must see patients at one of the three Near North clinics randomized to the intervention arm (Louise Landau, Komed Holman, Sunnyside).

Study medications. To select these drugs, we reviewed the top prescriptions ordered in 2013 by providers at Alliance FQHCs and selected those that have a Med Guide/REMS requirement. These drugs were reviewed by clinicians and pharmacists to ensure the list was comprehensive and appropriately reflects prescribing behaviors in the clinics. These drugs are diverse by class, indication, duration, side effects, route of administration, and potential for harm. Each has an FDA risk communication goal that presently is not being achieved.

Table 1.

STU#: 00201638

testosterone	escitalopram	sitagliptin and metformin
amiodarone	fluoxetine	exenatide
carbamazepine	paroxetine	liraglutide
divalproex	sertraline	pioglitazone
gabapentin	doxepin	rivaroxaban
lacosamide	imipramine	ciprofloxacin
lamotrigine	mirtazapine	levofloxacin
levetiracetam	colchicine	moxifloxacin
oxcarbazepine	emtricitabine and tenofovir	salmeterol
phenytoin	nevirapine	budesonide and formoterol
pregabalin	fenofibrate	fluticasone and salmeterol
topiramate	clopidogrel	celecoxib
valproic acid	alendronate	diclofenac
aripiprazole	risedronate	indomethacin
quetiapine	pimecrolimus	meloxicam
clonazepam	tacrolimus	sulindac
bupropion	amphetamine	dexlansoprazole
trazodone	methylphenidate	pantoprazole
desvenlafaxine	linagliptin	metoclopramide
duloxetine	saxagliptin	tamoxifen
venlafaxine	saxagliptin and metformin	varenidone
citalopram	sitagliptin	propylthiouracil

alprazolam	ibandronate	mometasone-formoterol
apixaban	lisdexamphetamine	nortriptyline
dexmethylphenidate	lorazepam	olanzapine
diazepam	lurasidone	tramadol
fluticasone-vilanterol		

Table 1 – part 2.

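### Research assistants can tell the arm from the clinic name when they recruit, and the same role sends IVR reminders and conducts the outcome interviews, with no masking or separation of tasks

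*Combined protocol and SAP*

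**What the plan says.** Allocation is by clinic (section 3.1): "Clinics will be randomized either to the intervention arm or to usual care". Section 3.2 lists the intervention clinics by name when it defines who may take the provider survey: "providers must see patients at one of the three Near North clinics randomized to the intervention arm".

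Under Method 1 in section 3.1, the daily report gives the RA "first and last name, date of birth, clinic name, phone number, preferred language, and date of index clinic visit". Method 2 supplies the "same data as listed in method 1, plus the name(s) of any study medications prescribed during the visit", and also the prescriber's name. The same section then says: "The RA will then call each patient, ask the few remaining eligibility questions to complete the screening process, invite the patient to participate". Consent is taken on that call.

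Only intervention patients are prompted to use the IVR system (section 9.3). If a patient has not used it after one day, an RA sends a reminder text; after two days, "the RA at Northwestern will call the patient to remind them to call into the system" (section 9.2).

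For outcomes, section 9.3 states that "the RA will administer the baseline interview via phone". Section 9.4 has the RA administer the adverse drug event questionnaire at 3 months, and section 28 (Non-English Speaking Subjects) describes RAs as able to conduct all the interviews. Section 8.1 makes knowledge and medication behaviour the primary endpoints.

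**The concern.** When patients are identified and invited after their clinic has been allocated, concealment at recruitment depends on the recruiter not knowing the arm. Here the recruiter is told the clinic. An RA who knows the arm may, without intending to, persist longer with some patients or judge eligibility differently.

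The same knowledge carries into the interviews. Knowledge and proper use are established by asking the patient questions over the phone, where tone, probing and the acceptance of a vague answer all leave room for influence. Self-reported adverse drug events are elicited in the same way, and the later judgement on whether a symptom is linked to the drug is not described as masked either.

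At stake is whether a difference between arms reflects the EMC2 strategy or partly reflects how patients were enrolled and questioned. Enrolling more patients does not remove this kind of error.

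**Working it through.** No figure in the plan bears on this point, so the check is to follow one patient through the stated procedures and ask at each step whether the RA can know the arm.

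1. **Before the first call.** Clinic determines arm (section 3.1), the intervention clinics are named (section 3.2), and clinic name is on the call list under both methods (section 3.1). The arm is known.

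2. **Screening and consent.** Allocation has already happened: section 9.1 notes that counselling and the printed summary are given at the visit, before any invitation. Two elements leave room for discretion. Section 25.1 ends contact after four weeks without a response but sets no number of attempts, and section 3.2 excludes patients who cannot complete follow-up interviews without giving an objective rule.

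3. **Baseline interview.** It is conducted by an RA (section 9.3). Because the in-clinic components came first, baseline knowledge is already measured after part of the intervention. It therefore cannot serve as a clean check on, or adjustment for, selective recruitment. For some patients baseline is also the final interview (section 22.4).

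4. **IVR reminders.** RAs send the text and make the call (section 9.2), and only intervention patients can need them (section 9.3).

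5. **The 4-week and 3-month interviews.** RAs conduct them. Intervention patients are asked whether they received summaries, IVR calls and nurse calls and how helpful these were (section 9.4). Those items reveal the arm to whoever asks them, and no item order is set. An RA who asks them at 4 weeks knows the arm at 3 months, the time point on which the sample size rests (section 11.2).

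6. **Scoring and event review.** Section 9.4 derives the knowledge score as the percentage correct, without saying who scores or from what record. It assigns the causality judgement to one reviewer, without saying whether arm is hidden. That judgement precedes the look-up of whether the event was reported through the IVR, so it could be made without knowing the arm.

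7. **Access to tracking data.** RAs share the tracking database (section 11.3), and no restricted view is described.

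The protocol contains no statement on masking of recruiters, interviewers, scorers or the event reviewer, and none that assigns these tasks to different staff.

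**The case against.** This is a pragmatic clinic-level trial in which patients and clinicians cannot readily be masked, and the plan has real safeguards. The call list comes from an EHR data pull and the RA is to call every patient on it (section 3.1). Cognitive exclusion uses a fixed screener (section 3.2), and the four-week contact limit applies to both arms (section 25.1). The consent script says only that patients might be asked to use the phone system (section 28.1). Knowledge is marked against the summary content, proper use has fixed components, and adverse events use a validated questionnaire (section 9.4). RAs are trained together and must show competence (section 11.4). These narrow the room for bias, but none hides the arm from the recruiter or interviewer.

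Several stronger readings are tempting and are not supported:

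- A reader might infer that RAs issue every IVR prompt. Section 9.2 names no sender for the first one; only the reminders are given to the RA, and only for patients who have not yet called in.
- A reader might infer that RAs mark the answers. Section 9.4 does not say so.
- A reader might infer that one individual does everything for a given patient. The documents assign the tasks to one role, and lack of separation is inferred from their silence.
- A reader might rank this as the chief source of bias in the trial. Nothing supports a ranking: patients are unmasked too, and fill and adherence are self-reported, which no change in RA duties would alter.

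The objection about staffing stands. Section 20.1 mentions a group of research assistants, section 20.2 a single bilingual one, and section 28 refers to bilingual RAs in the plural. No headcount is given, so a full split of roles cannot be assumed.

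**Conclusion.** The gap is real and should be closed. Following the procedures as written gives recruiters the arm before the first call and gives interviewers the arm before the outcomes are collected. Recruitment and the interviewer-collected outcomes (knowledge, proper use, self-reported adverse drug events) are therefore open to bias.

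Its direction and size are unknown. A reader might want to set some number of points against the 5.5-point difference in section 11.2, but that figure is a minimum detectable difference and says nothing about interviewer influence; any such ratio would only restate an assumption. Nor do the documents show that bias has occurred.

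The conclusion rests on two assumptions: that RAs can connect a clinic name to its arm, and that no unwritten arrangement already masks or divides these tasks.

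**What to change.** State in the protocol who is masked and at which step, and make these changes with existing staff:

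1. Withhold clinic and prescriber name from the recruiting RA until consent and the baseline knowledge and proper-use items are complete. The IVR upload needs these fields (section 11.3), but the prompt comes the day after baseline (section 9.2). Since section 23 plans equal numbers per arm, let the project manager track enrolment by clinic.
2. At every interview, ask the knowledge, proper-use and adverse event items before any item on counselling, print material, IVR or nurse calls.
3. Score knowledge and proper use, and review adverse event causality, from a file without arm or clinic.
4. Where RA numbers allow, have the 3-month interview done by an RA who neither sent that patient's IVR reminders nor asked the arm-revealing items at 4 weeks, and restrict that RA's view of the tracking database.
5. Report screening, refusal and enrolment by clinic and arm.

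Steps 1 to 3 and 5 change a report layout, the item order and data handling. Step 4 costs scheduling effort and depends on a headcount the documents do not give. Masking will remain incomplete whenever a patient mentions the IVR.
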